13.2 REPEATED OR UNSCHEDULED ASSESSMENTS OF SAFETY PARAMETERS

If a patient has repeated assessments prior to switch to this study, the last result prior to switch is used as baseline, except where otherwise specified. If post-baseline assessments are repeated or unscheduled, the last post-baseline assessment within a visit window is used as the study visit assessment for generating summary statistics. However, all post-baseline assessments are used for PCS value determination and all assessments are presented in the data listings.

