4.5.1. Hepatic Safety Monitoring

The guidelines described in this section are intended to enable early detection and action following abnormal liver function test (LFT) results. **It is the responsibility of the Investigator to expeditiously review LFTs, follow these guidelines and contact the Medical Monitor if a study subject meets any of the LFT abnormalities specified below.** In addition, repeat LFTs 2 to 3 times weekly, then weekly or less until abnormalities stabilize or return to within normal limits. LFTs should include the usual 4: ALT, AST, Tbili and ALP

Table 1: Summary of investigator actions with respect to Hepatic Monitoring

Repeat LFTs within 2 to 3 days if:	Discontinue Study Drug if:

 ALT or AST > 3 x ULN, or Tbili > 2 x ULN 	
 ALT or AST > 8 x ULN, or ALT or AST > 5 x ULN for > 2 weeks, or ALT or AST > 3 x ULN and (Tbili > 2 x ULN or INR > 1.5), or ALT or AST > 3 x ULN with appearance of fatigue, nausea, vomiting, right upper quadrant pain or tenderness, fever, rash, and/or eosinophilia (> 5%)

Abbreviations: ALP = alkaline phosphatase; ALT = alanine aminotransferase; AST = aspartate aminotransferase; GGT = gamma-glutamyl transferase; INR = international normalized ratio; LFT = liver function test; Tbili = total bilirubin; ULN = upper limit of normal.

If close monitoring for LFTs in a subject is not possible, study drug should be discontinued. Evaluate the subject for potential causes, which may include the following:

- Detailed history of symptoms and prior or concurrent diseases
- Concomitant drug use, including nonprescription medications, herbal and dietary supplements, alcohol or recreational drug use, or special diets
- Exposure to environmental chemical agents

- Rule out acute viral hepatitis Types A, B, C, D, E; autoimmune or alcoholic hepatitis; nonalcoholic steatohepatitis; hypoxic/ischemic hepatopathy; biliary tract disease
- Obtain additional tests as appropriate: eg, INR, GGT or direct bilirubin; ultrasound or other imaging to assess biliary tract disease
- Consider gastroenterology or hepatology consultations

Once LFTs return to normal, and depending on whether there is an explanation for the LFT elevations, study drug dosing may resume, after discussion with the Medical Monitor

Ref: FDA Guidance for Industry, titled: "Drug-Induced Liver Injury: Premarketing Clinical Evaluations", issued July 2009

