| 11.3 Vital Signs..... | 15 |
| 11.4 Electrocardiogram (ECG) | 15 |
| 12 References | 15 |
| 13 Appendix 1: Data Handling Conventions..... | 16 |
| 13.1 Visit Time Windows | 16 |
| 13.2 Repeated or Unscheduled Assessments of Safety Parameters | 17 |
| 13.3 Missing Date of Study Medication | 17 |
| 13.4 Missing Severity Assessment for Adverse Events..... | 17 |
| 13.5 Missing Relationship to Study Drug for Adverse Events | 17 |
| 13.6 Missing Date Imputation for Adverse Events | 17 |
| 13.7 Missing Date Imputation for Prior or Concomitant Medications..... | 19 |
| 13.8 Missing Date Imputation for last dose date..... | 20 |

| | | |
|------|---|----|
| 13.9 | Character Values of Clinical Laboratory Parameters..... | 20 |
|------|---|----|

LIST OF ABBREVIATIONS

| | |
|----------------|---|
| AE | Adverse Event |
| CTCAE | Common Terminology Criteria for Adverse Events |
| DSMB | Data and Safety Monitoring Board |
| ESA | Erythropoiesis-Stimulating Agent |
| FACT-An | Functional Assessment of Cancer Therapy – Anemia |
| Hb | Hemoglobin |
| HDL | High-Density Lipoprotein |
| IV | Intravenous |
| LDL | Low-Density Lipoprotein |
| MAP | Mean Arterial Pressure |
| MedDRA | Medical Dictionary for Regulatory Activities |
| PCS | Potentially Clinically Significant |
| PEY | Patient-Exposure-Year |
| RBC | Red Blood Cell |
| SAE | Serious Adverse Event |
| SAP | Statistical Analysis Plan |
| TEAE | Treatment Emergent Adverse Event |
| TIBC | Total Iron Binding Capacity |
| TLF | Tables, Listings, and Figures |
| TSAT | Transferrin Saturation |
| UACR | Urine Albumin-to-Creatinine Ratio |
| ULN | Upper Limit of Normal, value provided by the laboratory |

| | |
|--------------|--|
| WHODD | World Health Organization Drug Dictionary |
| WHO | World Health Organization |
| SOC | System Organ Class (used in MedDRA dictionary) |

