4.2 SAFETY ASSESSMENTS

Safety assessments include the following:

- Number (%) of subjects with AEs, serious adverse events (SAEs), and clinically significant changes in laboratory values from baseline observations
- Changes from baseline observations in vital signs and ECG findings, and clinical laboratory values, including Total Cholesterol, LDL cholesterol, LDL/HDL ratio, non-HDL cholesterol, HDL cholesterol TSAT, and Ferritin

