5.3 ADDITIONAL DATA HANDLING RULES AND PRESENTATION SPECIFICATIONS

The following general guidelines apply to all statistical analyses and data presentations:

- The baseline Hb value for efficacy analysis is defined as the mean of the central laboratory Hb value from the baseline visit at Day 1 (prior to receiving the first dose of study drug in this study), plus any other central lab Hb values within 15 days prior to Day 1
- Baseline of other assessments is defined as the last available value obtained prior to the first dose of study drug in this study, unless otherwise specified in this SAP.
- Analysis visits (instead of the nominal visits from CRF) derived from visit dates and visit time windows are used in all analyses, tables, listings and figures. Unscheduled visits within an allowable window are grouped into the closest scheduled visits based on the visit window specified in Appendix 1. For subjects who have more than one measurement at a scheduled visit, the last measurement issued, with the exception of CPK, WBC, liver function tests (i.e., ALT, AST, GGT, ALP, and total bilirubin), in which the maximum measurement issued.
- By default, US conventional units are used for laboratory value presentations. A set of lab summary tables in SI units are also provided based on TLF index.
- Age is calculated as of date that the informed consent form was signed.
 - age = INTCK('YEAR', Birth Date, Date of Informed Consent, 'C')where INTCK is a SAS function.
- Body weight, height and temperatures are converted using the following formula:
 - kg = lb/2.2
 - cm = 2.54 x in
 - C° = (5/9) x (F° – 32)
- For continuous variables that are recorded as “<X” or “>X”, the value of “X” issued in the calculation of summary statistics.
- The mean, standard deviation and median is presented with adding one more decimal to raw data with rounding off. The minimum and maximum is presented with the same number of decimals as in the raw data.
- All percentages are rounded to one decimal place and lined up by the decimal place. The percentage is suppressed when the count is zero.
- Any p-values are rounded to four decimal places and presented as ‘<.0001’ if they are less than 0.0001 before rounding.
- All tables and listings have a header showing “FibroGen, Inc.”, the protocol number, date of the database transfer, and Page x of y. A footer shows the program file path/name, output file path/name, run date and run time.

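### SAP 13.2 omits the liver-test exception made in SAP 5.3, so an ALT, AST or bilirubin peak that resolves within a visit window can drop out of the by-visit summary

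*SAP*

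**What the plan says.** SAP 5.3 places unscheduled values in visit windows: "Unscheduled visits within an allowable window are grouped into the closest scheduled visits based on the visit window specified in Appendix 1". Where a subject has more than one value at a visit it uses the last, "with the exception of CPK, WBC, liver function tests (i.e., ALT, AST, GGT, ALP, and total bilirubin), in which the maximum measurement issued" (the final word is read here as 'is used').

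SAP 13.2 covers the same situation for safety parameters: "the last post-baseline assessment within a visit window is used as the study visit assessment for generating summary statistics". Its phrase allowing for other specifications is attached to the baseline sentence only. It then adds that "all post-baseline assessments are used for PCS value determination and all assessments are presented in the data listings".

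Protocol 4.5.1 has abnormal liver tests repeated 2 to 3 times weekly, "then weekly or less until abnormalities stabilize or return to within normal limits". Its Table 1 sets ULN-multiple criteria for repeating tests and for discontinuing study drug.

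SAP 4.2 lists the number (%) of subjects with "clinically significant changes in laboratory values from baseline observations". PCS is expanded in the abbreviation list as "Potentially Clinically Significant", but no criteria follow. SAP 11.2 describes descriptive statistics and changes from baseline, and says that its list of parameters is not exhaustive. SAP section 1 places the table specifications in a separate document.

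**The concern.** Two programmers could each follow the SAP and produce different liver tables from the same data. The difference also has a direction. Repeats continue until values settle, so the last value in a window tends to be the settled one, and the last-value rule pulls the by-visit summary towards normal through the follow-up procedure itself.

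Liver safety has its own monitoring plan in this study and only 15 subjects entered, so one excursion may be the whole signal. An any-time count of abnormal values would guard against losing it. The SAP points towards such a count in 4.2 and 13.2 but does not define it.

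**Working it through.** The plan gives no figure to reproduce. The check sets the two rules side by side, then works out how many values compete within a window.

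**The rules.** Both sections share a default, the last value in the window. SAP 5.3 adds a named exception (CPK, WBC, ALT, AST, GGT, ALP, total bilirubin) and 13.2 does not repeat it. Both cover unscheduled values. The rules agree when the last value is also the highest and differ whenever an earlier value in the window is higher.

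**Windows and draws.** Inputs:

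- Analysis visits for serum chemistry: Weeks 4, 8, 12, then every 12 weeks; target day = 7 × week + 1 (SAP 13.1).
- Window: half the interval either side of the target day (SAP 13.1). Read literally, the Week 12 window (Days 43 to 127) overlaps the Week 8 window (Days 43 to 71), so midpoints between target days are used here.
- Scheduled liver tests: every 4 weeks (Protocol 7.1.1.1.3 and Appendix A).
- Longest planned duration: 312 weeks (SAP section 3).

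Results:

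- Week 24: target day 7 × 24 + 1 = 169. The interval to Week 36 is 84 days, so the window runs from Day 169 − 42 = 127 up to Day 169 + 42 = 211, a width of 84 days.
- Scheduled draws inside it: Week 20 (Day 141), Week 24 (Day 169) and Week 28 (Day 197), so three.
- Over 312 weeks: 312/4 = 78 scheduled draws and 3 + 25 = 28 windows. At one value per window, 78 − 28 = 50 scheduled values (50/78 = 64%) do not represent a visit. That count is the same under either rule; the rules decide which value is kept.

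**How often a peak is displaced (illustration).** Suppose an elevation is seen at exactly one of the three scheduled draws, is equally likely at each, and has no repeats. The last-value rule keeps it only if it falls at the third draw, so it is displaced with probability 2/3. Mandated repeats that return to normal within the same window would also displace a peak first seen at the third draw.

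**Effect on the summary (assumed data).** Take 15 subjects, 14 at 0.6 × ULN throughout and one with a peak that returns to 0.6 × ULN by the last draw in the Week 24 window. The mean under the maximum rule is (14 × 0.6 + peak)/15.

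| Peak (× ULN) | Maximum rule: mean | Maximum rule: highest value | Maximum rule: n above 3 × ULN | Last rule: mean | Last rule: highest value | Last rule: n above 3 × ULN |
|---|---|---|---|---|---|---|
| 3.5 | 0.79 | 3.5 | 1/15 | 0.60 | 0.60 | 0/15 |
| 5.5 | 0.93 | 5.5 | 1/15 | 0.60 | 0.60 | 0/15 |
| 8.5 | 1.13 | 8.5 | 1/15 | 0.60 | 0.60 | 0/15 |

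SAP 5.2 presents the minimum and maximum as well as the mean. The 5.3 rule would therefore show the excursion in the maximum column, and the 13.2 rule would remove it from there too.

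**The case against.** The strongest reply is that 5.3 is a deliberate, specific rule stated to apply to all analyses, and that it calls Appendix 1 additional. On that reading 13.2 merely restates the default and a cross-reference is missing. This is a natural reading, and it makes the problem a drafting omission rather than a wrong choice of analysis. But the SAP does not state it, and 13.2 is the section a programmer would consult for repeated safety values.

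The second reply is that the data are not lost. All values are listed and used for PCS determination. Protocol 10.6.4 flags out-of-range values in the listings. Protocol 11.3.6 allows clinically significant abnormalities that need active management to be reported as adverse events, which would bring them into the adverse event tables. With 15 subjects, a reader of the listings would probably notice a large peak. This stands and limits the impact to the by-visit summary. The PCS safeguard is weaker than it looks, because the SAP text gives it no criteria and section 11 no output.

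A reader might infer more than the documents support:

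- That the two rules are opposites. They share a default and differ by one named exception.
- That no hepatic thresholds are tabulated anywhere. The table specifications are in a document that was not available and may include them.
- That the maximum rule catches every elevation. With 4-weekly draws, a short elevation can fall between draws and be missed under either rule.
- That an elevation lasting D days is lost with probability 1 − D/84. That assumes every elevation is sampled and followed by a resolved value in the same window. Values below the Table 1 repeat triggers (ALT or AST >3 × ULN, Tbili >2 × ULN) generate no mandated repeats, and the 84-day width applies only from Week 24.

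**Conclusion.** The point holds as an unresolved inconsistency with a practical consequence. For liver tests, SAP 5.3 and 13.2 name different values for the same window, and nothing in the SAP settles which is used. If 13.2 is followed, a peak that resolves within a window disappears from the by-visit summary, its maximum included, but not from the listings.

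The two-thirds figure rests on three scheduled draws per window, one elevated draw equally likely at each position, and no repeats. It shows scale and is not an estimate for this study. The ALT values in the table are likewise assumed.

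The second part is narrower: the SAP text names a count of clinically significant laboratory changes and a PCS determination without criteria or a described output. Whether the separate table specifications supply them cannot be judged from these documents.

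**What to change.** In SAP 13.2, add to the post-baseline sentence: 'except CPK, WBC and liver function tests, for which the maximum in the window is used (Section 5.3)'.

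In SAP 11.2, add the following table, or cross-refer to the TLF document if it is already specified there. It gives the number (%) of subjects whose worst post-baseline value, over all assessments including unscheduled ones, meets each of:

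- ALT or AST >3 ×, >5 × and >8 × ULN;
- Tbili >2 × ULN;
- ALT or AST >3 × ULN with Tbili >2 × ULN, stating whether the two must be concurrent and, if so, within what interval.

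Describe these as laboratory cut-points drawn from protocol Table 1, not as the full Table 1 criteria. Table 1 attaches a duration of more than 2 weeks to the >5 × ULN criterion and also includes INR and symptom criteria. For the remaining parameters, state the PCS criteria or say where they are held.

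The cost is one clause and one small table or cross-reference. No new data are needed and no clinical rule changes.

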7.1.1.1.3. Every-4-Week Visit (± 3 days)

- Dose adjustment as needed
- Dispense roxadustat
- Vital signs: BP, HR, and respiratory rate
- Laboratory tests:
 - CBC with WBC differential and reticulocyte count
 - Fasting serum chemistry (with LFTs, lipid profile, and glucose)
 - Serum iron studies: iron, ferritin, transferrin (or TIBC), and TSAT
- Adverse events
- Concomitant medications

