10.1 ANALYSES OF EFFICACY ENDPOINTS

The following efficacy endpoints based on the observed data will be summarized at the analysis visits in Section 13.1:

- Mean Hb values over selected time ; mean Hb overlay mean weekly roxadustate dose over time plot.
- Number (%) of subjects with mean Hb at ≥ 10 g/dL averaged over selected time periods
- Number of rescue therapy events (composite of transfusions, IV iron, ESAs) of total PEY (defined as the sum of all subject's individual PEY) and number of individual rescue therapy modalities of total PEY (this can be expressed as per 100 PEY dependent on the magnitude of the result). PEY is defined as $(\text{last dose date} - \text{first dose date} + 1) / 365.25$
- Mean monthly oral iron dose (note the monthly dose is defined as sum of weekly dose over 4 weeks) at specific time periods
- Mean Reticulocyte hemoglobin content (CHr) at selected time points
- Mean Highly sensitive C-reactive protein (hs-CRP) at selected time points
- Mean Hepcidin levels in serum at selected time points
- Mean eGFR at selected time points
- Mean Total Cholesterol, LDL cholesterol, LDL/HDL ratio, HDL cholesterol, non-HDL cholesterol at selected time points

- Mean TSAT and Ferritin at selected time points

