13 APPENDIX 1: DATA HANDLING CONVENTIONS**13.1 VISIT TIME WINDOWS**

| Endpoint | Visits during Treatment Period | | | | |
|---|--------------------------------|-----------------------------|----------------------|---|------------------------------------|
| | Every 4 weeks ^a | Every 24 weeks ^b | Target Day | Analysis Visit Windows Actual Assessment Day ⁺ | Analysis Visit ⁺⁺ |
| | | | Day 1 | Day 1 | Baseline |
| BP, HR, respiratory rate* | X | | Day 7 * (Week #) + 1 | Target Day plus or minus half the duration to the next Target Day | Weeks 4, 8, 12 then every 12 weeks |
| 12-lead ECG | | X | Day 7 * (Week #) + 1 | [Target Day – 84, Target Day + 83] | Week 24, 48, ... |
| Hb, reticulocyte count, CHr* | X | | Day 7 * (Week #) + 1 | Target Day plus or minus half the duration to the next Target Day | Weeks 4, 8, 12 then every 12 weeks |
| CBC with WBC differential * | X | | Day 7 * (Week #) + 1 | Target Day plus or minus half the duration to the next Target Day | Weeks 4, 8, 12 then every 12 weeks |
| Fasting serum chemistry (including LFTs, lipid panel, glucose) | X | | Day 7 * (Week #) + 1 | Target Day plus or minus half the duration to the next Target Day | Weeks 4, 8, 12 then every 12 weeks |
| Serum iron, ferritin, transferrin (or TIBC), TSAT | X | | Day 7 * (Week #) + 1 | Target Day plus or minus half the duration to the next Target Day | Weeks 4, 8, 12 then every 12 weeks |
| Special labs (CHr, hepcidin, hs-CRP, plus exploratory biomarkers) ^l | | X | Day 7 * (Week #) + 1 | [Target Day – 42, Target Day + 41] | Week 24, 48, ... |
| 
Abbreviations: BP = blood pressure; CBC = complete blood count; CHr = reticulocyte hemoglobin content; CRP = C-reactive protein; ECG = electrocardiogram; HR = heart rate; LFT = liver function test; TIBC = total iron binding capacity; TSAT = transferrin saturation; WBC = white blood cell.
 
* Visit weeks are weekly (week 1 to 4), every 2 weeks (week 6 to 24), every 4 weeks afterwards
 
a Visit weeks may include of: Weeks 13, 37, 61, 85, 109, 133, 157, 181, 205, 229, and 253
 
b Visit weeks may include of: Weeks 25, 49, 73, 97, 121, 145, 169, 193, 217 and 241
 
++ Analysis visits are up to the EOT, which is the last day of treatment.
 
Note: The lower bound for the first visit window starts at Day 1.
 | | | | | |

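### Taking the last value in each 12-week window makes iron, lipid, eGFR and other chemistry summaries describe a draw about 4 weeks after their label, on the natural reading of the SAP's windows

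*SAP*

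**What the plan says.** - **Collection.** At every 4-weekly visit, Protocol 7.1.1.1.3 requires fasting serum chemistry (with lipids and liver tests) and "Serum iron studies: iron, ferritin, transferrin (or TIBC), and TSAT". Appendix A of the protocol agrees.
- **Windows.** SAP 5.3: "Analysis visits (instead of the nominal visits from CRF) derived from visit dates and visit time windows are used in all analyses". SAP 13.1 sets the target day at 7 × week + 1. For chemistry and iron, the window extends on either side of the target by half the distance to the next target day. The analysis visits are "Weeks 4, 8, 12 then every 12 weeks".
- **Choice of value.** SAP 5.3: "For subjects who have more than one measurement at a scheduled visit, the last measurement issued" (evidently meaning *is used*). The maximum is taken instead for CPK, WBC and the liver tests (ALT, AST, GGT, ALP, total bilirubin). SAP 13.2 has a last-value rule that opens with a condition, "If post-baseline assessments are repeated or unscheduled", and then states that "the last post-baseline assessment within a visit window is used as the study visit assessment for generating summary statistics". It does not carry over the maximum-rule exception. It adds that PCS determination and the listings use all post-baseline values.
- **Use.** SAP 10.1 summarises its list at the 13.1 analysis visits. The list includes lipids, eGFR and "Mean TSAT and Ferritin at selected time points".

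**The concern.** A last-value rule does little harm when a window is about as wide as the gap between draws, because the last value is then usually a repeat of the same visit. Here the window may be three times that gap. It then holds three separate scheduled draws, and the rule always prefers the latest over the one taken on the target day.

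Two things are at stake. The time label on the iron, lipid, eGFR and other last-value chemistry summaries may be wrong by a constant amount. In addition, most of the scheduled values would not reach those summaries. Iron utilisation is a stated exploratory objective, and SAP 3 reports only 15 subjects, so it matters which value represents each of them.

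**Working it through.** The plan gives no figure to reproduce, so the check lays the protocol's draw days over the SAP's windows.

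**Inputs.** Target day = 7 × week + 1 and analysis visits at Weeks 4, 8, 12, 24, 36, … (SAP 13.1). Draws every 4 weeks (Protocol 7.1.1.1.3). Treatment up to 312 weeks (Protocol 4.1). eGFR has no row in SAP 13.1; it is assumed to follow serum creatinine in the chemistry row.

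**Reading A: the next target day is the next analysis visit.**
- Week 24: target 7 × 24 + 1 = Day 169. The next target is Week 36, Day 253. Half the gap = (253 − 169)/2 = 42. The window is Day 127 to 211 (210 if windows may not touch).
- Draws inside it: Week 20 (Day 141), Week 24 (Day 169), Week 28 (Day 197). The last is Day 197, and 197 − 169 = **+28 days**.
- Likewise Week 36 takes Week 40, Week 48 takes Week 52 and Week 60 takes Week 64. The offset is +28 days in every complete window from Week 24.
- Week 12 (Day 85): with midpoint bounds the window is Day 71 to 126 and holds Weeks 12 and 16 (Days 85 and 113). It takes Day 113, again +28. With the literal symmetric width of 42 days it runs from Day 43 to 127 and overlaps the Week 8 window (Day 43 to 71).
- Weeks 4 and 8: one draw each with midpoint bounds, offset 0.

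**Share of draws used, Week 20 to Week 312.** Scheduled draws: (312 − 20)/4 + 1 = 74. Analysis visits: (312 − 24)/12 + 1 = 25. So 25 of 74 enter and 49 of 74 (66%) do not, which is two of three in each complete window.

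**Sensitivity.**
- Visit tolerance: the Week 28 draw, at ±3 days, falls on Days 194 to 200, inside the window. The next draw (Week 32, Day 225) comes no earlier than Day 222, outside it. The selected draw does not change.
- Missed draws, assumed independent with probability p: mean offset in weeks = [4(1 − p) − 4p²(1 − p)]/(1 − p³). This gives 3.8, 3.6 and 3.1 weeks at p = 5%, 10% and 20%.

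**Reading B: the next target day is the next 4-weekly visit.** The Week 24 window is 169 ± 14, about Day 155 to 182. It holds only the Day 169 draw, so the offset is 0. Weeks 20 and 28 still enter no 12-weekly summary.

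**What a window mean would add.** The documents give no within-subject correlations, so these are assumptions, together with stable levels, N = 15 and a single baseline value.
- Mean change: SE ratio = √[(1 + v)/2], where v is the variance of the mean of three draws relative to one. With correlation ρ between adjacent draws (first-order autoregressive), v = (3 + 4ρ + 2ρ²)/9. For ρ = 0, 0.3, 0.5: v = 0.333, 0.487, 0.611; ratio = 0.816, 0.862, 0.898; reduction = 18%, 14%, 10%.
- Mean level: SE ratio = √[ICC + (1 − ICC)/3]. ICC 0.5 gives 0.816 (18%); ICC 0.8 gives 0.931 (7%).

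**The case against.** - **The rules may not reach these draws.** SAP 13.2 is limited to repeated or unscheduled assessments of safety parameters, and SAP 5.3 speaks of several measurements at one scheduled visit. Neither says that three scheduled visits collapse into one. This stands as a criticism of relying on 13.2 alone. But 5.3 makes window-derived visits apply to all analyses, so its last-value rule is the one a programmer would use. If it does not apply, the SAP has no rule for these draws, which also needs correcting.
- **The window definition is ambiguous.** Chemistry and iron are marked in the 4-weekly column, and a footnote there lists Weeks 13, 37, 61 and so on, which settles nothing. The ECG window of about 84 days either side is half its 24-week reporting interval, which fits Reading A, but ECGs are also collected 24-weekly. A reader might infer that the plan certainly reports the wrong draw. The documents support that only under Reading A.
- **The values are not discarded.** A reader might infer that two-thirds of the results go unused. SAP 13.2 sends every value to PCS determination and the listings. The omission concerns by-visit summaries as the SAP describes them; the table specifications are in a separate document.
- **The precision argument is weak.** The 18% figure needs independent draws for change, or an ICC as low as 0.5 for level. It also assumes stable levels, in which case a draw 28 days late does not bias the mean. Mistiming and lost precision therefore cannot both be claimed at full strength, and a 12-week average is a different quantity from a value at a time point. This stands.
- **Importance.** SAP 4.1 does not list these laboratory parameters as efficacy endpoints. Lipids, TSAT and ferritin are safety assessments in 4.2 and eGFR is exploratory in 4.3, although 10.1 analyses them all under efficacy. Nor would the change align them with dose, which SAP 8.1 averages over 8-week and later 12-week periods. Both points stand.

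**Conclusion.** The point holds conditionally. With windows built on the listed analysis visits and full attendance, the last-value summaries labelled Week 12, 24, 36 and so on describe the draw 28 days later, although an on-target draw exists. From Week 24, two of three scheduled draws then do not enter the by-visit statistics. Under 4-weekly windows the timing is right, but the intermediate draws are still left out of the 12-weekly summaries.

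The exact 28 days also assumes no later unscheduled draw in the window and no cut-off by end of treatment. CPK, WBC and liver tests are not affected under 5.3. The study is descriptive, with no power calculation, so the importance is minor to moderate. The case for change rests on correct labelling and an unambiguous rule more than on precision.

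**What to change.** - **SAP 13.1:** state that the next target day is the next analysis visit in the table, with bounds at the midpoints between neighbouring targets. This also removes the overlap between Weeks 8 and 12.
- **SAP 5.3 and 13.2:** for continuous parameters not under the maximum rule, replace the last measurement with the one closest to the target day, with a stated tie-break. Make clear that the rule covers several scheduled draws in one window. With full attendance the offset falls from +28 days to 0.
- **SAP 13.2:** carry over the maximum-rule exception from 5.3. Keep the existing use of all values for PCS determination and listings.
- **Optional:** add a supplementary summary using the mean of all on-treatment central values in the window. It is centred on the label from Week 24 and uses all three draws. Under the assumptions above it narrows the SE by roughly 7% to 18%, but it smooths short-lived changes.

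The cost is SAP wording and one programming rule, with no new data. The closest-value rule alone still uses one draw in three.
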